#### **4.1.3 Safety follow-up**

After discontinuation of study treatment, all patients will be followed for safety for at least 30 days except in case of death, loss to follow-up or withdrawal of consent. For details please refer to [Section 7](#).

#### **4.1.4 Efficacy follow-up**

Patients who discontinue treatment for reasons other than disease progression will continue to be followed every 8 weeks for efficacy (i.e., tumor assessments and selected patient reported outcomes) during the first 18 months and every 12 weeks until 36 months, then change to as clinically indicated until disease progression, death, withdrawal of consent, loss to follow-up, or subject/guardian decision. If a patient starts a new antineoplastic treatment without withdrawing consent, the patient should continue to be followed for efficacy according to above

specified protocol schedule until disease progression, death, withdrawal of consent, loss to follow-up, or subject/guardian decision. For further details please refer to [Table 7-1a](#) and [Section 7](#).

#### **4.1.5 Survival follow-up**

All patients will be followed for survival once they discontinue study treatment and efficacy evaluations until the final number of OS events have been reached or the study is stopped for other reasons. Survival follow-up will be conducted every 12 weeks or earlier if a survival update is required to meet safety or regulatory needs. Survival information can be obtained by clinical visits or telephone calls until death, the patient is lost to follow-up, or the patient withdraws consent for survival follow-up.

During the survival follow up, in addition to vital status, all subsequent anti-neoplastic therapies initiated after study treatment discontinuation will be collected along with the start/end date and date of disease progression on subsequent therapies [REDACTED]

## **4.2 Timing of interim analyses and design adaptations**

There is no planned efficacy interim analysis for the primary PFS endpoint. Interim analyses for OS will be conducted if PFS is statistically significant as detailed in [Section 10.5.1](#) and [Section 10.7.2](#).

## **4.3 Definition of end of the study**

The end of treatment (EOT) for a given patient is defined as when the patient permanently discontinues all study treatment and all the end of treatment procedures are completed. The end of study (EOS) for a given patient is defined as when the patient discontinues from follow-up assessments as detailed in [Table 7-1a](#).

If the primary endpoint, PFS, is statistically significant at the primary PFS analysis, data collection will continue during survival follow-up and End of Study will be declared after the final number of OS events are reached (or earlier if OS reaches statistical significance at any of the interim analyses for OS) and after all patients have completed the safety follow-up period (30 days after treatment discontinuation).

If the primary endpoint, PFS, is not statistically significant at the primary PFS analysis then End of Study will be declared after all patients have discontinued all components of study therapy and completed the safety follow-up period (30 days after treatment discontinuation).

Patients continuing to derive benefit from study treatment at the end of the study in the opinion of the investigator will be able to continue receiving trial therapy on a separate protocol. Alternatively Novartis will provide study treatment to the investigator as per local regulations.

Following the statistically significant OS benefit demonstrated at the second OS analysis, with protocol amendment 6, study participants are unblinded, with an opportunity for those patients still on study treatment in the placebo combination arm to cross-over to the LEE011 combination arm. Crossover is optional and will be conducted only upon documented consent of the study patient. The study will be closed when all study patients have either discontinued

study treatment and completed the safety follow-up period, withdrawn consent, are lost to follow-up, or as soon as arrangements are made for ongoing access to study treatment for all patients still on study treatment, whichever happens first.

#### 4.4 Early study termination

The study can be terminated at any time for any reason by Novartis. Should this be necessary, the patient should be seen as soon as possible and the same assessments should be performed as described in [Section 7.1.5](#) for a discontinued or withdrawn patient. The investigator may be informed of additional procedures to be followed in order to ensure that adequate consideration is given to the protection of the patient's interests. The investigator will be responsible for informing IRBs and/or ECs of the early termination of the trial.

### 5 Population

#### 5.1 Patient population

The study will include pre-menopausal women with HR+, HER2-negative, advanced breast cancer who received no prior hormonal therapy for advanced breast cancer and are eligible for endocrine therapy. The investigator or designee must ensure that only patients who meet all the following inclusion and none of the exclusion criteria are offered treatment in the study.

Written informed consent must be obtained prior to any screening study-related procedures.

#### 5.2 Inclusion criteria

Patients eligible for inclusion in this study have to meet **all** of the following criteria:

1. Patient is an adult, female  $\geq 18$  years old and  $< 60$  years old at the time of informed consent and has signed informed consent before any trial related activities are conducted and according to local guidelines.
2. Confirmed negative serum pregnancy test ( $\beta$ -hCG) before starting study treatment or patient has had a hysterectomy.
3. Patient is premenopausal or perimenopausal at the time of study entry.
  - Premenopausal status is defined as either:
    - Patient had last menstrual period within the last 12 months,
  - OR**
  - If on tamoxifen or toremifene within the past 14 days, plasma estradiol and FSH must be in the premenopausal range per local normal range,
  - OR**
  - In case of therapy induced amenorrhea, plasma estradiol and/or FSH must be in the premenopausal range per local normal range.
- Patients who have undergone bilateral oophorectomy are not eligible.
- Perimenopausal status is defined as neither premenopausal nor postmenopausal (see exclusion criteria 3).

4. Patient has advanced (locoregionally recurrent or metastatic) breast cancer not amenable to curative therapy (e.g. surgery and/or radiotherapy).
5. Patients who received **(neo) adjuvant therapy** for breast cancer are eligible:
  - If the patient has never received any prior endocrine therapy **OR** if  $\geq 12$  months have elapsed since the patient's last dose of adjuvant therapy, then the patient is eligible to receive tamoxifen + goserelin **or** a NSAI + goserelin for advanced breast cancer based on the investigator's choice.
  - If tamoxifen or fulvestrant was the last prior (neo) adjuvant therapy and the last dose was given  $< 12$  months prior to randomization, then the patient is eligible to receive a NSAI (letrozole or anastrozole) + goserelin for advanced breast cancer.
  - If letrozole, anastrozole, or exemestane was the last prior (neo) adjuvant therapy and the last dose was given  $< 12$  months prior to randomization, then the patient is eligible to receive tamoxifen + goserelin for advanced breast cancer.
6. Patients who received  $\leq 14$  days of tamoxifen or a NSAI (letrozole or anastrozole) with or without goserelin or goserelin  $\leq 28$  days for advanced breast cancer prior to randomization are eligible. Patients must continue treatment with the same hormonal agent + goserelin during the study. No treatment interruption is required for these patients prior to randomization.

**Note:** Patients who are receiving goserelin for reasons other than for advanced breast cancer treatment are eligible (e.g endometriosis). Patients who received  $\leq 28$  days goserelin for advanced breast cancer are eligible.
7. Patients who have received up to 1 line of chemotherapy for advanced breast cancer and have been discontinued 28 days before randomization are eligible.

**Note:** If a cytotoxic chemotherapy regimen was discontinued for reasons other than disease progression and lasted less than 21 days, this regimen does not count as a prior line of chemotherapy.
8. Patient has a histologically and/or cytologically confirmed diagnosis of estrogen-receptor positive and/or progesterone receptor positive breast cancer by local laboratory (based on most recently analyzed biopsy).
9. Patient has HER2-negative breast cancer (based on most recently analyzed biopsy) defined as a negative in situ hybridization test or an IHC status of 0, 1+ or 2+. If IHC is 2+, a negative in situ hybridization (FISH, CISH, or SISH) test is required by local laboratory testing.
10. Patient must have either:
  - Measurable disease, i.e., at least one measurable lesion as per RECIST 1.1 criteria.

**OR**

  - If no measurable disease is present, then at least one *predominantly* lytic bone lesion must be present (patients with no measurable disease and only one *predominantly* lytic bone lesion that has been previously irradiated are eligible if there is documented evidence of disease progression of the bone lesion after irradiation).
11. Patient has ECOG PS 0 or 1.
12. Patient has adequate bone marrow and organ function as defined by the following laboratory values (as assessed by central laboratory):

- Absolute neutrophil count  $\geq 1.5 \times 10^9/L$ .
  - Platelets  $\geq 100 \times 10^9/L$ .
  - Hemoglobin  $\geq 9.0$  g/dL.
  - Potassium, sodium, calcium (corrected for serum albumin), and magnesium within normal limits of the central laboratory or corrected to within normal limits with supplements before the first dose of study medication
  - INR  $\leq 1.5$ .
  - Serum creatinine  $< 1.5$  mg/dL.
  - In absence of liver metastases, alanine aminotransferase (ALT) and aspartate aminotransferase (AST) should be below  $2.5 \times$  ULN. If the patient has liver metastases, ALT and AST should be  $< 5 \times$  ULN.
  - Total serum bilirubin  $< ULN$ ; or total bilirubin  $\leq 3.0 \times ULN$  with direct bilirubin  $< 1.5 \times ULN$  of the central laboratory in patients with well documented Gilbert's Syndrome.
13. Must be able to swallow study therapy
14. Subjects must be able to communicate with the investigator and comply with the requirements of the study procedures.
15. Must be willing to remain at the clinical site as required by the protocol visit evaluation schedule.

### 5.3 Exclusion criteria

Patients eligible for this study must not meet **any** of the following criteria:

1. Patient who has received a prior CDK4/6 inhibitor.
2. Patient has a known hypersensitivity to any of the excipients of LEE011 or goserelin or hormonal treatment assigned (tamoxifen or a NSAID (letrozole or anastrozole)).
3. Patient is postmenopausal. Postmenopausal status is defined either by:
  - Prior bilateral oophorectomyOR
  - Age  $\geq 60$OR
  - Age  $< 60$  and amenorrhea for 12 or more months (in the absence of chemotherapy, tamoxifen, toremifene, or ovarian suppression) and FSH and estradiol in the postmenopausal range per local normal range.
  - If taking tamoxifen or toremifene, and age  $< 60$ , then FSH and plasma estradiol level in postmenopausal ranges per local laboratory normal range.

**Note:** For women with therapy-induced amenorrhea, serial measurements of FSH and/or estradiol are needed to ensure menopausal status ([NCCN Guidelines Version 3.2014](#)).
4. Patients who currently have inflammatory breast cancer at screening.

5. Patients who received any prior hormonal anti-cancer therapy for advanced breast cancer, except for  $\leq 14$  days of tamoxifen or NSAID or goserelin  $\leq 28$  days for advanced breast cancer prior to randomization.
6. Patient who has not had resolution of all acute toxic effects of prior anti-cancer therapy to NCI CTCAE version 4.03 Grade  $\leq 1$  (except alopecia or other toxicities not considered a safety risk for the patient at investigator's discretion).
7. Patient has a concurrent malignancy or malignancy within 3 years of randomization, with the exception of adequately treated basal cell skin carcinoma, squamous cell skin carcinoma, non-melanomatous skin cancer or curatively resected cervical cancer.
8. Patient with CNS metastases.  
**Note:** CNS involvement must be ruled out by assessments if a patient has any signs or symptoms indicating potential CNS metastases.
9. Patient has impairment of gastrointestinal (GI) function or GI disease that may significantly alter the absorption of the study drugs (e.g., ulcerative diseases, uncontrolled nausea, vomiting, diarrhea, malabsorption syndrome, or small bowel resection).
10. Patient has a known history of HIV infection (testing not mandatory).
11. Patient has any other concurrent severe and/or uncontrolled medical condition that would, in the investigator's judgment, contraindicate patient participation in the clinical study (e.g., chronic pancreatitis, chronic active hepatitis, etc.).
12. Clinically significant, uncontrolled heart disease and/or cardiac repolarization abnormality, including any of the following:
  - History of angina pectoris, symptomatic pericarditis, myocardial infarction, or coronary artery bypass graft (CABG) within 6 months prior to study entry
  - Documented cardiomyopathy
  - Left Ventricular Ejection Fraction (LVEF)  $< 50\%$  as determined by Multiple Gated acquisition (MUGA) scan or echocardiogram (ECHO)
  - Clinically significant cardiac arrhythmias (e.g., ventricular tachycardia), complete left bundle branch block, high-grade AV block (e.g., bifascicular block, Mobitz type II and third degree AV block)
  - Long QT syndrome or family history of idiopathic sudden death or congenital long QT syndrome, or any of the following:
    - Risk factors for Torsades de Pointe (TdP) including uncorrected hypokalemia or hypomagnesemia, history of cardiac failure, or history of clinically significant/symptomatic bradycardia
      - resting heart rate  $< 50$  at rest, by the triplicate ECG
      - resting heart rate  $> 90$  at rest, by the triplicate ECG
      - Systolic blood pressure  $> 160$  or  $< 90$  mmHg
      - On screening, inability to determine the QTcF interval on the ECG (ie: unreadable or not interpretable) or QTcF  $> 450$  msec (using Fridericia's correction). All as determined by the average of the triplicate screening ECG, per central review.

13. Patient is currently receiving any of the following substances and cannot be discontinued 7 days prior to the start of the treatment:
  - Known strong inducers or inhibitors of CYP3A4/5, including grapefruit, grapefruit hybrids, pomelos, star-fruit, and Seville oranges.
  - Medications with a known risk to prolong the QT interval or induce Torsades de Pointes that cannot be discontinued or replaced by safe alternative medication (e.g. within 5 half-lives or 7 days prior to starting study drug).
  - Medications that have a narrow therapeutic window and are predominantly metabolized through CYP3A4/5.
  - Additionally, for patients receiving tamoxifen: known strong inducers or inhibitors of CYP2D6.
  - Herbal preparations/medications and dietary supplements (except for vitamins).
14. Patient has had major surgery within 14 days prior to starting study drug or has not recovered from major side effects.
15. Patient is currently receiving warfarin or other Coumadin derived anti-coagulant, for treatment, prophylaxis or otherwise. Therapy with heparin, low molecular weight heparin (LMWH), or fondaparinux is allowed.
16. Patient is currently receiving or has received systemic corticosteroids  $\leq 2$  weeks prior to starting study drug, or who have not fully recovered from side effects of such treatment. **Note:** The following uses of corticosteroids are permitted: single doses, topical applications (e.g., for rash), inhaled sprays (e.g., for obstructive airways diseases), eye drops or local injections (e.g., intra-articular).
17. Patient is concurrently using other antineoplastic agents (except for patients who are receiving  $\leq 14$  days of tamoxifen or NSAID or goserelin  $\leq 28$  days for advanced breast cancer prior to randomization).
18. Patient who has received radiotherapy  $\leq 4$  weeks or limited field radiation for palliation  $\leq 2$  weeks prior to randomization, and who has not recovered to grade 1 or better from related side effects of such therapy (with the exception of alopecia) and/or if  $\geq 25\%$  of the bone marrow was irradiated.
19. Pregnant or nursing (lactating) women, where pregnancy is defined as the state of a female after conception and until the termination of gestation, confirmed by a positive hCG laboratory test.
20. Women of child-bearing potential, defined as all women physiologically capable of becoming pregnant, **unless** they are using highly effective methods of contraception during dosing of study treatment and for 21 days after stopping study medication. Highly effective contraception methods include:
  - Total abstinence (when this is in line with the preferred and usual lifestyle of the subject. Periodic abstinence (e.g., calendar, ovulation, symptothermal, post-ovulation methods) and withdrawal are not acceptable methods of contraception.
  - Total hysterectomy or tubal ligation at least six weeks before taking study treatment.
  - Male sterilization (at least 6 months prior to screening). For female subjects on the study, the vasectomized male partner should be the sole partner for that subject.
  - Combination of the following:

- a. Placement of an intrauterine device (IUD) or intrauterine system (IUS)
  - b. Barrier methods of contraception: Condom or Occlusive cap (diaphragm or cervical/vault caps) with spermicidal foam/gel/film/cream/ vaginal suppository
21. Participation in a prior investigational study within 30 days prior to enrollment or within 5-half lives of the investigational product, whichever is longer.
  22. Not able to understand and to comply with study instructions and requirements.
  23. Patient with symptomatic visceral disease or any disease burden that makes the patient ineligible for endocrine therapy per the investigator's best judgment

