#### 1.2.1.1.2 Safety pharmacology and toxicology

*In vivo* cardiac safety studies demonstrated a signal for QT prolongation with the potential to induce incidences of premature ventricular contractions (PVCs) at higher exposure levels.

The effects of LEE011 on the bone marrow (hypocellularity), lymphoid system (lymphoid depletion), intestinal mucosa (atrophy), skin (atrophy), bone (decreased bone formation) and testes (atrophy) are considered to be related to the pharmacological inhibition of cell replication in these tissues due to CDK4/6 inhibition.

[figure not shown]
An increased number of ovarian corpora lutea was observed in a single female dog in the 4-week toxicity study at the highest dose tested (20 mg/kg/day) and this effect could also be related to the pharmacology of LEE011 (arrest of estrous cycle).

The liver, bile system and gall bladder (proliferative changes, cholestasis, sand-like gallbladder calculi and inspissated bile) and the kidney (concurrent degeneration and regeneration of tubular epithelial cells) were identified as additional target organs of toxicity which are not likely related to the primary pharmacology of LEE011.

Inflammatory changes in the lungs of dogs were considered secondary to aspiration of test article and are indicative of the irritant potential of the formulated test-article in the respiratory tract. Correlating hematological and/or biochemistry changes were seen for the effects described in the bone marrow, lymphoid system and liver.

Generally all changes demonstrated either reversibility or a clear tendency towards reversibility. In the rat, there was no evidence of teratogenicity however LEE011 was embryofetotoxic. Data from a rabbit embryofetal development study, shows that LEE011 is teratogenic in the rabbit in the absence of maternal toxicity.

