Patients who are currently taking placebo in combination with tamoxifen (and goserelin), that request cross over to LEE011 combination treatment, must switch their endocrine partner from tamoxifen to an NSAI; either letrozole or anastrozole per Investigator decision, prior to crossing over to LEE011. There needs to be a 35-day (5 half-lives) washout period from tamoxifen before starting LEE011, during which time the patients will be taking NSAI plus goserelin only. The rationale for this change in the background endocrine therapy is based on the increased incidence of significant QT prolongation events for the combination of tamoxifen and LEE011 observed in the primary analysis of this study and, as such, the combination of ribociclib and tamoxifen is not recommended. This consideration does not apply to patients originally randomized to LEE011 plus tamoxifen and remaining on study treatment, as for those patients

any QT prolongation events have been managed via LEE011 dose modifications (Table 6-5). Those patients on the placebo arm who do not wish to cross-over from placebo to LEE011 can remain on their current treatment allocation.

All of the study treatment cross-over changes will be managed by the study IRT system. Endocrine partner treatment will be managed locally.

Unblinded study treatment period will conclude once a patient discontinues from the study treatment for any reason or the EOS is declared, whichever occurs first.

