#### **6.3.1.1 Tamoxifen**

The established clinical dose of tamoxifen (20 mg/day) will be used in each arm and no dose modification of tamoxifen is planned in this study.

Following protocol amendment 6, patients who are currently taking placebo in combination with tamoxifen (and goserelin) and wish to cross over to the LEE011 combination treatment, must switch their endocrine partner from tamoxifen to an NSAID; either letrozole or anastrozole. A washout period of 5 half-lives (35 days) from tamoxifen is needed before LEE011 can be initiated, during which period the patient will be receiving NSAID and goserelin only.

For information on tamoxifen and management of tamoxifen related adverse events refer to the Tamoxifen SmPC or Prescribing Information.

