### **8.4 Pregnancies**

To ensure patient safety, each pregnancy occurring while the patient is on study treatment must be reported to Novartis within 24 hours of learning of its occurrence. The pregnancy should be followed up to determine outcome, including spontaneous or voluntary termination, details of the birth, and the presence or absence of any birth defects, congenital abnormalities, or maternal and/or newborn complications.

Pregnancy should be recorded on a Clinical Trial Pregnancy Form and reported by the investigator to the oncology Novartis Chief Medical Office and Patient Safety (CMO&PS). Pregnancy follow-up should be recorded on the same form and should include an assessment of the possible relationship to the investigational treatment any pregnancy outcome. Any SAE experienced during pregnancy must be reported on the SAE Report Form.

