### **10.1.2 Safety set**

The Safety Set includes all patients who received at least one dose of study medication defined as tamoxifen/NSAI, goserelin, LEE011 or placebo. Patients will be analyzed according to the study treatment they actually received. Actual treatment refers to the treatment that the patient was randomized to, unless the alternative treatment was received throughout the trial.

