3.5.1 Duration of study treatment exposure

The duration of exposure to study treatment will be calculated as

Duration of exposure to study treatment (days) = (*last date of exposure* to any study treatment component) – (date of first administration of study treatment) + 1.

Duration of exposure to any single component of study treatment will be calculated as

Duration of exposure (days) = (last date of exposure to study treatment component) – (date of first administration of study treatment component) + 1.

The *last date of exposure* is defined as follows for the study treatment components:

- For ribociclib/placebo, tamoxifen, anastrozole, and letrozole: the last date of exposure is defined as the date of last administration of the corresponding medication;
- For goserelin, the last date of exposure is defined as the date of last administration of goserelin + 27 days.
 - If a patient died or was lost to follow-up within date of last administration + 27 days, then the last date of exposure is the date of death or last contact date, respectively.

The duration of exposure includes the periods of temporary interruption (of any component of the study treatment for any reason). The duration of study treatment exposure will be summarized by treatment arm. In addition, the duration of exposure to study treatment will be categorized into time intervals (e.g., <3 months; 3-<6 months; 6-<9 months, etc); frequency counts and percentages will be presented for the number of patients in each interval.

For analyses related to the cross-over on-treatment period, duration of exposure of cross-over open-label ribociclib plus NSAID plus goserelin treatment will be calculated as above considering the combination of drugs ribociclib plus NSAID plus goserelin administered during the cross-over on-treatment period.

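### Section 8.4 requires pregnancy reporting only while the patient is on treatment, although contraception is required for 21 days and safety data are collected for at least 30 days after the last dose

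*Protocol*

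**What the plan says.** Criterion 20 in Protocol Section 5.3 excludes women of child-bearing potential unless they are "using highly effective methods of contraception during dosing of study treatment and for 21 days after stopping study medication". The protocol summary carries the same 21 days.

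Section 8.4 sets the reporting duty: "each pregnancy occurring while the patient is on study treatment must be reported to Novartis within 24 hours of learning of its occurrence". It also asks for a Clinical Trial Pregnancy Form and follow-up to outcome. It states no period after the last dose.

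The neighbouring safety rules run longer:
- Section 8.1.1 continues adverse event monitoring for at least 30 days after the last dose.
- Section 8.2.2 requires every serious adverse event to be reported for at least 30 days after treatment stops. Later events are reportable only if the investigator suspects a causal link.
- Section 8.2.1 counts a birth defect as serious.
- Section 7.1.7 lists pregnancy among the reasons for ending post-treatment follow-up, entered on a disposition page.

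Section 1.2.1.1.2 reports that LEE011 harmed embryos and fetuses in rats and that "LEE011 is teratogenic in the rabbit in the absence of maternal toxicity".

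**The concern.** Participants must be under 60 and pre- or perimenopausal, and the investigational drug has a documented animal reproductive hazard. The protocol therefore asks for contraception beyond the last dose. It does not ask to be told when contraception fails in that same period.

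What is at stake is fetal-exposure data. An uncomplicated pregnancy conceived shortly after the last dose would enter no pregnancy record, and nobody would be bound to learn its outcome. Whatever pregnancy data the sponsor holds for this drug would be complete for conceptions on treatment and haphazard just after it.

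**Working it through.** **1. Windows side by side, in days after the last dose**

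| Rule | Days covered |
|---|---|
| Required contraception (Protocol 5.3, criterion 20) | 21 |
| Adverse event monitoring (8.1.1) | at least 30 |
| Serious adverse events regardless of causality (8.2.2) | at least 30 |
| Default on-treatment window for safety tables, no crossover (final-report SAP, 2.1.8) | 30 |
| Pregnancy reporting (8.4) | none stated |

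Gap against contraception: 21 − 0 = 21 days. Gap against safety collection: 30 − 0 = 30 days.

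**2. A worked case: conception on day 10.** Day 10 is inside the 21 days and inside the 30 days. The patient is no longer on study treatment, so Section 8.4 imposes nothing. Pregnancy as such is not a seriousness criterion in Section 8.2.1, so Section 8.2.2 imposes nothing either unless a serious event occurs. A birth defect would come to light long after day 30, and would then be reportable only on suspicion of causality. The last scheduled pregnancy test is at the end-of-treatment visit (Table 7-1a), which Section 7.1.5 places within 15 days of stopping. At least days 16 to 21 of required contraception therefore follow the last scheduled test.

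**3. Is LEE011 itself still clearing in the gap?** Section 1.2.1.5 gives a mean effective half-life of 12.3 to 42.9 hours across the doses tested. Five half-lives are 5 × 12.3 / 24 = 2.6 days to 5 × 42.9 / 24 = 8.9 days. At the slow end, roughly the first nine days after the last dose lie inside five LEE011 half-lives and outside Section 8.4. Both values are well under 21 days.

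**4. The 21 days against the other drugs.** Section 1.3 gives a tamoxifen half-life of about 5 to 7 days.
- 5 × 7 = 35 days reproduces the washout in Sections 6.1 and 6.3.1.1; 5 × 5 = 25 days is the lower end.
- 21 days falls short by 35 − 21 = 14 days, or 25 − 21 = 4 days.
- 21 days is 21/7 = 3.0 to 21/5 = 4.2 half-lives, leaving 0.5^3.0 = 12.5% to 0.5^4.2 = 5.4% of parent drug.
- Letrozole (half-life 2 days) needs 5 × 2 = 10 days, and anastrozole (50 hours) 5 × 50 / 24 = 10.4 days. Both fit within 21.
- For goserelin, take the implant on cycle day 1 and all dosing stopping on cycle day d. The gap to day 28 is max(0, 28 − (d + 21)): 6 days at d = 1, 1 day at d = 6, and 0 from d = 7.

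**5. Which last dose starts the clock?** Criterion 20 uses *study treatment* for the dosing period and *study medication* for the 21 days, and defines neither there. Section 6.1 defines study treatment as the triple combination. Section 10.1.2 reads study medication broadly ("at least one dose of study medication defined as tamoxifen/NSAI, goserelin, LEE011 or placebo"), but only to define the safety set. Section 6.1.4 lets a patient stop LEE011 or placebo and continue tamoxifen or an NSAI. If study medication is read as LEE011 alone, the 21 days can end while the oral partner continues. If it is read as any component, they start only after the partner stops.

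**The case against.** The strongest objection to the reporting point is that other routes exist. Serious events are reportable for 30 days and later if causality is suspected, a birth defect is serious by definition, and pregnancy is a listed disposition reason. This stands against a reading that a reader might reach, that pregnancies after the last dose need never be reported. It does not close the gap. Neither route requires an uncomplicated pregnancy to be notified within 24 hours or followed to outcome.

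A reader might also infer that the 21 days are too short because study drug is still present. The documents do not support that:
- Section 6.3.1.1 says "A washout period of 5 half-lives (35 days) from tamoxifen is needed before LEE011 can be initiated", but this governs crossover from placebo, and Section 6.1 gives QT prolongation as the reason. It is not a competing contraception rule.
- The final-report SAP, Section 3.5.1, ends tamoxifen exposure at its last administration.
- The animal hazard cited is LEE011's, and five LEE011 half-lives fall within 21 days. The documents cite no reproductive toxicity for tamoxifen or goserelin. Section 6.1 defers the marketed drugs to local labels, which are not included.
- The same SAP section says "For goserelin, the last date of exposure is defined as the date of last administration of goserelin + 27 days". A reader might conclude that 7 of 28 goserelin days go uncovered. The gap arises only if all dosing stops on cycle days 1 to 6. It is then at most 6 days, and it vanishes if stopping is counted from that SAP exposure date.

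Finally, the 114 patients still on treatment at Amendment 7 might be taken as the number affected. They are not split by endocrine partner or by ability to conceive, so that number is unknown.

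**Conclusion.** The reporting mismatch holds. Section 8.4 leaves uncovered the whole 21 days in which contraception is required, and at least 30 days of safety follow-up. It does so even for the first nine days or so, in which LEE011 may still be clearing. This rests on reading Section 8.4 as written, with a pregnancy conceived after the last dose not counted as occurring on treatment. The number of pregnancies missed is probably small and cannot be estimated from the documents. The point concerns completeness of safety data and does not touch the efficacy analyses.

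The contraception wording is a secondary matter. Criterion 20 does not say which drug's last dose starts the 21 days, and 21 days is shorter than the 35 days used for tamoxifen in another context. These passages need reconciling; they do not show that 21 days is wrong.

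**What to change.** In Section 8.4, let pregnancy reporting run from first dose to the end of the required post-treatment contraception period, and at least to the end of the 30-day safety follow-up. Written that way, the rule follows whatever contraception period the sponsor sets.

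In criterion 20 and the matching text in the protocol summary, use one term and state which component's last dose starts the clock, including for patients who stop LEE011 and continue tamoxifen or an NSAI. The sponsor should reconcile this with the tamoxifen washout in Sections 6.1 and 6.3.1.1, or record why the two periods differ. No duration is proposed here.

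The cost is wording in the next amendment and in the consent form, plus a few more pregnancy forms. No extra visit is needed.
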